Our **hypotheses** are the following:

Hypothesis 1: ACTH gel is superior to no treatment in maintaining remission in children with frequently relapsing or steroid dependent nephrotic syndrome.

Hypothesis 2: Relapses in children with frequently relapsing or steroid dependent nephrotic syndrome receiving ACTH gel will increase when the dose of ACTH gel is reduced by 50%.

Hypothesis 3: ACTH gel will increase the percentage of children with frequently relapsing or steroid dependent nephrotic syndrome that remain relapse free off medication.

Primary end-points:

The primary end-point related to Hypothesis 1 is the proportion of patients in each arm with a relapse during the initial 6 months of treatment.

The primary end-point related to Hypothesis 2 is the proportion of relapse-free patients during the first 6 months and second 6 months of treatment with ACTH. This will include patients initially randomized to ACTH and patients who receive ACTH as rescue therapy following their initial relapse in patients randomized to no treatment.

The primary end-point related to Hypothesis 3 is the proportion of patients who have relapses in the 6 months following completion of one year of ACTH. This will be compared to the

proportion of patients with relapses during the initial 6 months in the patients randomized to no treatment.

Secondary end-points:

Our secondary end-points are the following:

1. The total prednisone exposure over the initial 12 months in the two groups.
2. The number of relapses over the initial 6 months in the two groups.
3. The change in BMI, height SDS, and cholesterol over the study period for both groups

Study Design and Methods

The experimental design is a multi-center, prospective, controlled open label, randomized trial comparing ACTH gel and no treatment in preventing relapses in pediatric patients with frequently relapsing or steroid dependent nephrotic syndrome.

Patients will be randomized in a 1:1 ratio to either no treatment or treatment with ACTH gel. The primary outcome will be the presence of a relapse within 6 months of starting ACTH gel or no treatment.

After initial recruitment, enrollment will begin with a screening visit to determine eligibility and obtain informed consent and assent. Randomization and weaning of all other medications for the treatment of NS will begin after remission has been achieved for those with active relapse. There will be a 2 week overlap of ACTH and current immunosuppressive medications:

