1. ACTH will be initiated 2 weeks prior to the completion of the prednisone taper for patients who are receiving prednisone at the time of consent.
2. ACTH will be initiated 2 weeks prior to stopping preventive medications such as tacrolimus, cyclosporin, and mycophenolate.

Patients randomized to no treatment will be followed for up to 6 months or until disease relapse, whichever occurs first. Patients who relapse within 6 months will be given the option of reassignment to the ACTH treatment group after remission has been achieved using conventional corticosteroid therapy.

Patients randomized to ACTH treatment will be given ACTH for 12 months. During the second 6 months, the ACTH dose will be reduced to 50% of the starting dose. The outcome of interest is the presence of relapses after dose reduction. Follow-up will occur throughout the 12 months of therapy, and also for 6 months following the completion of ACTH therapy. The outcome of interest is the percentage of patients with relapses in the 6 months after completing a 12 month course of ACTH treatment.

Visits

Screening visit: The study will be explained to the patient and family. Inclusion and exclusion criteria will be reviewed to determine eligibility. Consent and assent will be obtained as appropriate. Medical history will be recorded. A physical exam will be performed. If indicated, a

plan for prednisone tapering will be explained to the family. The date of the baseline visit will either be determined at that visit or via telephone for patients who are currently in relapse.

Baseline visit: The patient will be seen and have baseline labs (renal function panel, cholesterol, urinalysis, urine protein/creatinine ratio). A urine pregnancy test will be performed in females of childbearing age (achieved menarche) who are randomized to ACTH treatment along with counseling in required birth control. An interval medical history and quality of life (QOL) survey will be performed. Patients will have a physical examination. Patients will be randomized to either ACTH gel or no treatment. Patients will be given Albutix and instructions for daily monitoring of the urine and recording the results. Patients randomized to ACTH gel will receive their first injection in clinic and be taught how to perform injections at home. A stop date for other immunosuppressive medications will be provided, if appropriate, 2 weeks after starting ACTH.

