ACTH Treatment ACTH will be dosed by body surface area (BSA), with an initial dose of 80U per 1.73m². After 6 months of treatment, the initial dose will be reduced by 50% (1st reduction), to complete the second 6 months of ACTH therapy.

If patients develop significant side effects on the initial dose, they will have an early dose reduction by 50% at the discretion of each individual site PI (1st reduction). They will complete a total 6 months of treatment with the initial and reduced dose. After 6 months, ACTH will be reduced again by 50% (2nd reduction), to complete the second 6 months of ACTH therapy.

Patients who do not tolerate ACTH therapy despite an early dose reduction will exit the study with reporting of adverse events as appropriate.

Patients who relapse on a reduced dose of ACTH during the second 6 months of treatment will have their dose reverted to the previous dose and complete a total of 12 months of treatment with no further dose reductions.

Patients with two relapses on the highest tolerated ACTH dose will exit the study.

| BSA | Initial Dose | 1st Reduction (50%) | 2nd Reduction (25%) |
|------------|---------------------|----------------------------|----------------------------|
| 0.50-0.60 | 24U = 0.3mL | 12U = 0.15mL | 8U = 0.1mL |
| 0.61-0.75 | 32U = 0.4mL | 16U = 0.2mL | 8U = 0.1mL |
| 0.76-0.95 | 40U = 0.5mL | 20U = 0.25mL | 12U = 0.15mL |
| 0.96-1.09 | 48U = 0.6mL | 24U = 0.3mL | 12U = 0.15mL |
| 1.10-1.25 | 56U = 0.7mL | 28U = 0.35mL | 16U = 0.2mL |
| 1.26-1.45 | 64U = 0.8mL | 32U = 0.4mL | 16U = 0.2mL |
| 1.46-1.60 | 72U = 0.9mL | 36U = 0.45mL | 20U = 0.25mL |
| ≥ 1.61 | 80U = 1.0mL | 40U = 0.5mL | 20U = 0.25mL |

*Note: there is rounding of the doses to the closest administrable amount by subcutaneous injection.

Interval Visits

Telephone contact will occur weekly for the first 3 weeks after randomization. This will include screening for adverse events, reviewing medications and timing of medication changes, review of Albustix testing, and reviewing dosing of ACTH if applicable. Patients randomized to ACTH treatment will have two additional telephone contacts one month after ACTH dose reduction or discontinuation. This is to screen for symptoms of adrenal insufficiency.

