Follow-up visits in patients randomized to ACTH will occur 1 month, 2 months, 4 months, 6 months, 8 months, 10 months, 12 months, 15 months and 18 months after the baseline visit. An interval medical history (including screening for adverse events) will be performed. Patients will have a physical examination. A renal function panel, cholesterol, urinalysis, urine protein/creatinine ratio, and QOL survey will be obtained at months 6 and 12. Urine pregnancy test, if applicable, will be obtained at months 4 and 8.

[figure not shown]
The dose of ACTH will be reduced by 50% after 6 months of treatment. Patients who have significant side effects attributed to ACTH will have an earlier dose reduction (i.e., before 6 months) at the discretion of each individual site PI. The PI will be asked to review possible side effects with the patient at each visit and decide if a dose reduction is warranted. A telephone contact will be made 1 month after dose reduction to screen for symptoms of adrenal insufficiency.

Relapses will be treated with prednisone, at 2mg/kg/day or 60mg/m²/day (maximum dose 60 mg) until remission is achieved, with a subsequent taper off therapy over 4 weeks. For patients receiving a reduced dose of ACTH, the dose will be reverted back to the last effective dosage on which remission was sustained, and continue at that dose until the end of the study. If >1 relapse occurs on the initial ACTH dose, ACTH therapy will be considered a failure and terminated.

The total ACTH therapy duration will be 12 months, after which, the subjects will be seen at follow-up at 15 and 18 months.

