Patients who are randomized to no treatment will have follow-up visits up to the time of relapse, at 1 month, 2 months, 4 months, and 6 months. An interval medical history (including screening for adverse events) will be performed. Patients will have a physical examination. A renal function panel, cholesterol, urinalysis, and urine protein/creatinine ratio, and QOL survey will be obtained at month 6. They will be treated with prednisone for any relapses and have the option to be placed on ACTH during the last 2 weeks of the prednisone taper if the relapse occurred within 6 months of the baseline visit. The subsequent visit schedule and procedures will be identical to the schedule for subjects initially randomized to ACTH (i.e., it will include a baseline visit, telephone contacts, and 18 months of follow-up). Alternatively, the patient may elect to be treated via standard of care in collaboration with the treating nephrologist, and the patient will then exit the study.

Flow Chart of Study Course

Participant Selection

Sixty subjects will be recruited from 10-12 large pediatric centers. Subjects may also be identified via physician or self-referral from advertisements placed on NephCure. Additionally, subjects may be recruited from registries of individuals interested in research participation.

Patients and their caregivers will be approached during a relapse of nephrotic syndrome or within 4 months of a relapse. The following criteria will be reviewed during the screening visit to determine eligibility:

Inclusion criteria

1. Age >1 year at onset of nephrotic syndrome
2. Age 2-20 years at time of randomization
3. Estimated GFR > 50 ml/min/1.73 m² at most recent measure prior to randomization (Schwartz formula)
4. Steroid responsive nephrotic syndrome throughout clinical course (never required a second agent to attain remission of a relapse of nephrotic syndrome)
5. History of frequently relapsing or steroid dependent nephrotic syndrome (defined as 2 or more relapses within 6 months after initial therapy or 4 or more relapses in any 12 month period OR relapse during taper or within 2 weeks of discontinuing prednisone).
6. Patient is currently in relapse of nephrotic syndrome or had a relapse within the last 4 months (defined as an increase in the first morning urine protein to creatinine ratio ≥ 2 or Albustix reading of ≥ 2 for 3 or 5 consecutive days).

Exclusion criteria

1. Prior treatment with ACTH.

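### Secondary end-points are compared as randomised, but no-treatment follow-up ends at first relapse or month 6: 12-month prednisone cannot be compared, and relapse count, cholesterol, BMI and height are incomplete in part of that arm

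*Combined protocol and SAP*

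**What the plan says.** Study Design and Methods limits observation of the control arm: "Patients randomized to no treatment will be followed for up to 6 months or until disease relapse, whichever occurs first". Interval Visits repeats the limit: "Patients who are randomized to no treatment will have follow-up visits up to the time of relapse". The visits fall at months 1, 2, 4 and 6, each with a physical examination. Of the laboratory work it says: "A renal function panel, cholesterol, urinalysis, and urine protein/creatinine ratio, and QOL survey will be obtained at month 6". A control who relapses within 6 months may start ACTH in the last 2 weeks of the prednisone taper, with a new baseline visit and 18 months of follow-up on the ACTH schedule. A control who prefers standard care leaves the study.

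The ACTH arm has visits to month 18, with cholesterol at months 6 and 12. ACTH Treatment adds: "Patients with two relapses on the highest tolerated ACTH dose will exit the study". Interval Visits says instead: "If >1 relapse occurs on the initial ACTH dose, ACTH therapy will be considered a failure and terminated". The second passage ends therapy, not study participation.

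The secondary end-points are:
- "The total prednisone exposure over the initial 12 months in the two groups"
- "The number of relapses over the initial 6 months in the two groups"
- "The change in BMI, height SDS, and cholesterol over the study period for both groups"

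Statistical Analysis compares prednisone, relapse number, cholesterol and BMI change as randomised, by two-sample t-test or a non-parametric alternative. Height SDS is summarised descriptively by time point. The list of tested end-points is introduced as examples, so it may not be complete. The text does not say how exits or data after a switch enter these comparisons. The flow chart is not available to check.

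**The concern.** The follow-up rule suits a time-to-first-relapse outcome. The secondary end-points need information after the first relapse, or after month 6, and the plan stops collecting it in one arm for reasons tied to outcome. The result is differential missing data and unequal observation windows. Switching to ACTH is a separate matter: in an as-randomised comparison it only dilutes the difference.

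The introduction rests the case for ACTH partly on sparing children the effects of steroids on growth, bone and weight. Prednisone exposure, BMI, height and cholesterol are where the trial could show that. Data not collected at the time are hard to recover later.

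**Working it through.** **Inputs.** From Statistical Analysis: 30 patients per arm and 6-month relapse rates of 70% (no treatment) and 30% (ACTH). The plan gives no power or sample size for the secondary end-points. Its one power figure, 91% for the primary end-point, reproduces: two looks at the stated boundaries give 91.7% by normal approximation. The share of relapsing controls who switch to ACTH is not given, so I take 0 to 100%.

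**Who is observed.** Expected relapsing controls: 30 × 0.70 = 21. Relapse-free: 30 − 21 = 9.

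| Share switching | Observable for 12-month prednisone | Full 6-month relapse count |
|---|---|---|
| 0% | 0 of 30 | 9 of 30 |
| 50% | 10.5 of 30 | 9 + 10.5 = 19.5 of 30 |
| 100% | 21 of 30 | 30 of 30 |

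The 9 relapse-free controls lack months 6 to 12 in every row, and each control observed to month 12 has relapsed and taken ACTH.

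**Visits on the no-treatment schedule.** With a constant hazard (assumption), the expected number still on schedule at month m is 30 × 0.3^(m/6): 24.5, 20.1, 13.4 and 9.0 at months 1, 2, 4 and 6. About 30 − 24.5 = 5.5 relapse before any post-baseline visit. If they exit, they contribute no change in BMI or height.

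**Cholesterol.** The month-6 draw reaches only the 9 relapse-free controls, a group selected on outcome. Switchers are drawn at the new baseline and 6 and 12 months later. Under the same hazard, the median relapse time among relapsers solves 0.3^(t/6) = 1 − 0.35, so t = 6 × 0.431/1.204 = 2.15 months. Adding 1, 2 or 4 weeks to remission (assumption) and 2 weeks of taper puts the new baseline at a median of 2.8, 3.1 or 3.5 months. The first on-ACTH draw then falls at 8.8, 9.1 or 9.5 months after randomisation, and at 6.7 months at the earliest. More switching therefore does not supply a month-6 on-ACTH value.

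**BMI and height.** Switchers are examined at the new baseline and each later visit. With the timing above, 97-100% of them have an examination within 1 month of month 6 from randomisation, and all have one within 1 month of month 12. Only exiters lose these measures. The windows still differ: at most 6 months on no treatment, against visits to month 18 in the ACTH arm.

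**Relapse count.** An exiting control stops at 1, while an ACTH patient can reach 2. In a simple Poisson model (no gap after relapse, ACTH counts uncapped), the means are −ln(0.3) = 1.204 for control and −ln(0.7) = 0.357 for ACTH. If every relapsing control exits, the recorded control mean is 0.70. The difference shrinks from 1.204 − 0.357 = 0.847 to 0.70 − 0.357 = 0.343, a loss of 59%.

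Simulation adds the cap of 2 on ACTH and a risk-free gap after each relapse (30 per arm, two-sided 5%). It assumes that truncated counts are analysed as if complete. For an inert drug, by t-test:

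| Share switching | Called worse |
|---|---|
| None, gap 1.5-2 months | about 22-29% |
| None, gap 0.25-1 month | about 35-47% |
| Half | about 7-10% |
| All | about 1-3% (called better in up to 6% with short gaps) |

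Mann-Whitney gives 18-23% with no switching and a 1.5-2 month gap. With complete 6-month counts, both tests give about 2-3% per side. Under the planned effect ACTH is never called worse. At the 1.5-2 month gap, t-test power rises with complete counts from 78-80% to 94-95% (no switching) and from 82-83% to 90-91% (half), and stays at about 86% with full switching.

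**The case against.** A reader might infer that the whole control arm is lost for all four end-points. The documents do not support that. Switchers remain in the study for 18 months from their new baseline, relapse-free controls have a complete count of zero and month-6 BMI and cholesterol, and only exiters lose relapse counts, BMI and height. That part of the objection stands, and the point is limited accordingly.

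The simulated error rates are also conditional. The text nowhere says that truncated counts would be treated as complete, and it gives no switching share. The gap after relapse is an assumption too. The plan defines steroid dependence by relapse during the taper or within 2 weeks of stopping, so a long risk-free gap may be optimistic. The figures show the direction and possible size of the problem and are not bounds.

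Interval Visits speaks of treating any relapse in controls and makes the ACTH option conditional on relapse within 6 months, which could imply that later relapses are seen. No visit or contact after month 6 is described for a relapse-free control, however, so this does not rescue 12-month prednisone.

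Finally, these are secondary end-points without stated power, no hypothesis rests on them, and under the planned effect truncation understates the benefit. That limits the stakes but does not make the 12-month comparison possible.

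**Conclusion.** The point holds, to a different degree for each end-point. Followed exactly, the plan cannot deliver 12-month prednisone as randomised at any switching share: at least 9 of 30 controls are missing by design, and the 0 to 21 who can be observed are selected on relapse and treated with ACTH. The relapse count, BMI and height are incomplete for exiters only. Month-6 cholesterol is missing for all of the roughly 21 relapsing controls. Change over the study period covers different lengths of time in the two arms.

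These counts rest on the plan's own 70% rate. The error rates for the relapse count rest further on the assumed gap, the assumed switching share and truncated counts being analysed as complete.

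It would be wrong to conclude that the main result is compromised. The primary end-point needs only the first relapse within 6 months, which is captured before a control switches or exits. The control proportion used for Hypothesis 3 is the same quantity. This should be fixed, but it does not threaten the primary analysis.

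**What to change.** Reconcile Secondary end-points, Study Design and Methods, ACTH Treatment, Interval Visits and Statistical Analysis. Treatment, switching and treatment-exit rules need not change. Separate leaving treatment from leaving data collection, and settle whether two relapses on ACTH end therapy or study participation.

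- **Collection.** Record relapses and prednisone for every randomised patient to month 6 from randomisation, in both arms, regardless of relapse, switch or exit. Keep a chart or telephone prednisone log to month 12 for all, so that the stated 12-month end-point is delivered.
- **Window.** Define change in BMI, height SDS and cholesterol over a common 6 months from randomisation, with height, weight and a cholesterol draw at month 6 for everyone.
- **Analysis.** State that these comparisons are as randomised and include data after switching. The planned t-test or non-parametric test is then adequate. Any sensitivity analysis that stops at the switch should use time at risk, because counts cut at the switch bring the truncation back.

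**Cost.** A protocol amendment and SAP wording. One month-6 visit with a blood draw for about 21 relapsing controls, including switchers, whose own visits run from a later baseline. The same for a few ACTH-arm exits: about 1 patient is expected to have two relapses by month 6 (30 × 0.024 to 0.030 = 0.7 to 0.9), plus intolerance exits at a rate not given. Log contacts to month 12 for relapse-free controls and exiters. Families who leave for standard care must agree to continued data collection. The downside is dilution if most relapsers switch: relapse-count power by t-test is about 86% at full switching, against 90-95% at half or none (1.5-2 month gap).

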2. Cyclophosphamide or rituximab within the last 4 months.
3. Lactation, pregnancy, or refusal of birth control (abstinence qualifies) in females with child-bearing potential.
4. Planned treatment with live or live-attenuated vaccines once enrolled in the study.
5. Participation in another therapeutic trial concurrently or 30 days prior to randomization.
6. Active/serious infection (including, but not limited to Hepatitis B or C, HIV).
7. Malignancy concurrently or within the last 2 years.
8. Systolic or diastolic blood pressure >95% for age/height while receiving maximal doses of 3 or more medications.
9. Prior diagnosis of diabetes mellitus (Type I or II) or fasting glucose >200mg/dL
10. Organ transplantation
11. Contraindications to Acthar: scleroderma, osteoporosis, systemic fungal infections, ocular herpes simplex, recent surgery, history of or the presence of peptic ulcer, congestive heart failure, uncontrolled hypertension, primary adrenocortical insufficiency, or adrenal cortical hyperfunction
12. Secondary cause of nephrotic syndrome (e.g., SLE)
13. Biopsy demonstrating a diagnosis other than minimal change, FSGS or a variant (mesangial proliferation, IgM nephropathy)
14. Inability to consent/assent

Statistical Analysis

The primary end-point of the study and on which the statistical power is based is the proportion of patients who have a relapse in the 6 months following randomization to either ACTH or no ACTH.

We hypothesize that the 6 month relapse rate for patients receiving no treatment is 70%. In order to detect a 6 month relapse rate of 30% for patients receiving the ACTH gel, we will randomize 30 patients in each arm using a two sided z test with $\alpha=.05$. Our statistical power to detect such a difference is 91% which assumes two interim analyses at 50% and 100% of accumulated information. That is, once 30 patients have 6 month relapse data, we will conduct the first interim analysis. The last one will be completed once we have relapse data on all 60 patients. The table below gives the operating characteristics for such a design:

| Number of Patients with 6 Months Data | Boundary p-value |
|--|-------------------------|
| 30 | 0.006 |
| 60 | 0.045 |

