Using the method of Lan-DeMets, we list the boundary p-value for this sequential design. Thus, after our first interim look, we will reject the null hypothesis of equal 6 month relapse rates between ACTH gel and no treatment if our test statistic renders a p-value $< .006$. According to the intent to treat principle, patients will be analyzed according to the treatment they have been assigned to during the randomization procedure. The odds ratio of ACTH versus no ACTH, plus the Wald 95% confidence interval, will be also be calculated.

The primary end-point related to specific aim 2 is the proportion of relapse-free patients during the first 6 months and second 6 months of treatment with ACTH. This will include patients initially randomized to ACTH and patients who receive ACTH as rescue therapy following their initial relapse. We will estimate 6 month and 12 month relapse-free rate using the method of Kaplan-Meier and compare treatments using a log-rank test.

The primary end-point related to specific aim 3 is the proportion of patients who have relapses in the 6 months following completion of one year of ACTH. This will be compared to the proportion of patients with relapses during the initial 6 months in the patients randomized to no treatment using a z test statistic. Odds ratios of ACTH vs no ACTH will also be calculated.

We will also compare patients as randomized by secondary endpoints such as total prednisone exposure in 12 months, number of relapses, cholesterol and change in BMI with two sample t-tests. If normality assumptions do not hold, appropriate non-parametric methods will be used.

Growth data collected during the study will be summarized descriptively for each treatment group at each time point. Based on height data collected during the study and published reference height information, the height standard deviation score (SDS, also called z-score) will be computed for each patient at each time point as:

$$(\text{Height} - \text{mean height for that age category}) / \text{SD of height for that age category}.$$

Descriptive statistics of this endpoint will be presented by time point and the z-scores will allow identification of potential outliers.

Treatment Assignment and Randomization

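### The only pregnancy test and birth-control counselling at baseline depend on assignment to ACTH, so a failure of exclusion 3 can come to light after randomisation and in one arm

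*Combined protocol and SAP*

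**What the plan says.** - **Exclusion criteria, item 3** carries no restriction by arm: "Lactation, pregnancy, or refusal of birth control (abstinence qualifies) in females with child-bearing potential".
- **Screening visit:** "Inclusion and exclusion criteria will be reviewed to determine eligibility". The Participant Selection section repeats this before its list of criteria: "The following criteria will be reviewed during the screening visit to determine eligibility". The screening visit lists consent, history and examination, but no pregnancy test.
- **Baseline visit:** "A urine pregnancy test will be performed in females of childbearing age (achieved menarche) who are randomized to ACTH treatment". Counselling on birth control is attached to the same group, those "who are randomized to ACTH treatment along with counseling in required birth control". Randomisation takes place at this visit: "Patients will be randomized to either ACTH gel or no treatment".
- **Interval Visits, ACTH schedule:** "Urine pregnancy test, if applicable, will be obtained at months 4 and 8". The no-treatment schedule lists no pregnancy test. Controls who relapse and choose ACTH go through a baseline visit under the ACTH procedures.
- **Statistical Analysis:** "patients will be analyzed according to the treatment they have been assigned to during the randomization procedure".

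The documents do not say what happens, in follow-up or in the analysis, to a randomised girl whose test is positive or who then declines birth control.

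**The concern.** An eligibility rule that covers everyone should be verified for everyone before assignment. Here the review is common to all candidates, but the only objective check of pregnancy, and the only counselling on birth control that the protocol describes, wait until the arm is known. An ineligible girl assigned to ACTH may be discovered; one assigned to no treatment would not be discovered by any planned baseline procedure.

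At stake is the comparability of the arms for the primary end-point in an open-label trial of 30 per arm. If a late failure leads a girl to leave, the ACTH arm loses patients through a process that has no counterpart among controls. If she stays in the analysis without receiving ACTH, the ACTH arm is diluted. The plan does not say how either case is handled.

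**Working it through.** **1. Order of events**

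| Step | Who | Exclusion 3 checked how |
|---|---|---|
| Screening | All candidates | Criteria reviewed; no test listed |
| Wait for remission, if in relapse | Those in relapse | Nothing listed |
| Baseline, randomisation | All | Nothing before assignment is described |
| Baseline, after assignment | ACTH arm, past menarche | Urine test and counselling |
| Baseline, after assignment | No-treatment arm | Nothing listed |
| Months 4 and 8 | ACTH schedule | Urine test, if applicable |
| Second baseline | Controls who switch to ACTH | As for the ACTH arm |

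A test given to those randomised to ACTH cannot be done until assignment is known, even though the paragraph mentions it before the randomisation sentence. The second baseline for switching controls follows the relapse that is already their primary end-point event, so it does not make the randomised comparison symmetrical. For patients enrolled in relapse, randomisation waits for remission, so their status can also change after the screening review.

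**2. How many girls could be concerned**

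The age range is 2 to 20 years, so post-menarchal girls can enrol; their number is not given. Assume they are 10–20% of 60 patients: 6–12 girls, or 3–6 per arm at 1:1. How many of these would fail exclusion 3 at baseline after passing screening cannot be derived from the documents. The calculations below take one or two purely as illustrations.

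**3. The plan's own power**

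Inputs from Statistical Analysis: 70% versus 30%, 30 per arm, two-sided z test, boundary p-values 0.006 and 0.045, stated power 91%.

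- Fixed design, unpooled variance: SE = √(2 × 0.21/30) = 0.1183; 0.40/0.1183 = 3.381; Φ(3.381 − 1.960) = 92.2%.
- Two looks with the stated boundaries: 91.7% with unpooled variance, 88.5% with pooled variance.

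The stated 91% is reproduced to within a point by the unpooled version.

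**4. If the girl is dropped from the ACTH arm**

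Start from the planned 9/30 = 30.0%.

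- One who would have relapsed: 8/29 = 27.6%.
- One who would not have relapsed: 9/29 = 31.0%.
- Two who would have relapsed: 7/28 = 25.0%.

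The shift can go either way. Two-look power with pooled variance goes from 88.5% to 87.9% with one dropped and 87.3% with two.

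**5. If she is kept in the ACTH arm untreated**

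Assume that she relapses at the control rate of 70%.

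- One: (29 × 0.30 + 0.70)/30 = 9.4/30 = 31.3%. The planned difference falls from 40.0 to 38.7 points.
- Two: (28 × 0.30 + 1.40)/30 = 9.8/30 = 32.7%. The difference is 37.3 points.

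Fixed-design unpooled power, using SE = √(0.21/30 + p(1 − p)/30):

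- One: p = 0.3133, SE = 0.1190, 0.3867/0.1190 = 3.248, Φ(3.248 − 1.960) = 90.1%.
- Two: p = 0.3267, SE = 0.1197, 0.3733/0.1197 = 3.118, Φ(3.118 − 1.960) = 87.7%.

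Both compare with 92.2% when nobody is affected.

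**The case against.** The strongest reply has three parts.

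- **Screening comes first.** All criteria, including exclusion 3, are reviewed for every candidate before randomisation. Refusal of birth control needs only a question, abstinence qualifies, and the later counselling can be read as instruction for girls who have already accepted the requirement. This stands. A reader might infer that the exclusion is applied only after randomisation and in one arm, or that eligibility goes unchecked in half the trial. The documents do not support that: what is late and one-sided is the test and the counselling. Nor do they support a view that refusal is likelier to surface than pregnancy.
- **Intent to treat answers it.** A reader might also infer that a late failure is removed from the analysis. No section says so, and the analysis rule keeps her in her assigned arm. This stands too, so exclusion bias is a risk left open by silence and not a planned procedure. The rule does not remove the dilution shown above.
- **The test has an evident purpose.** It accompanies the first injection, and controls who switch are covered by their own baseline visit. That explains testing by exposure. It does not explain why a criterion set for both arms is objectively verified in only one.

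**Conclusion.** The point holds as a minor weakness in how eligibility is verified. Exclusion 3 is reviewed for all at screening, but its objective check comes after assignment and, for the randomised comparison, only in the ACTH arm. The fate of a girl who fails at that stage is not stated.

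The likely size is small. One patient moves the ACTH rate by about 1 to 2.4 points, and in the illustrations two move it by at most 5 points, against a planned difference of 40. With one patient, power falls by about half a point if she is dropped and about two points if she is kept untreated. These figures rest on the planned 70% and 30% rates, on control-rate relapse in an untreated patient, and on illustrative counts. The expected number of late failures cannot be estimated from the documents. No systematic direction of bias from dropping patients has been shown. The reason to act is that the asymmetry is avoidable at almost no cost.

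**What to change.** In the Baseline visit paragraph, carry out the existing urine test and confirm the birth-control requirement of exclusion 3 for every post-menarchal girl before the randomisation envelope is opened. The Screening visit, Baseline visit and Exclusion criteria sections would then agree, and both arms would be verified in the same way before assignment.

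Add one sentence to Statistical Analysis: a patient found after randomisation not to meet exclusion 3 stays in her assigned arm for the primary analysis. This only makes the existing intent-to-treat rule explicit for the case.

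The cost is one reordered step and additional tests in girls who are then assigned to no treatment: about 3–6 under the 10–20% assumption. Urine is already collected from every patient at this visit for urinalysis and protein/creatinine ratio, so no new visit or sample is needed. Sample size, test and boundaries are unchanged.
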